8.5.6. Adverse Events of Special Interest

Any newly identified malignancy or case of active TB occurring after the first study intervention administration(s) in participants participating in this clinical study must be reported by the investigator to the sponsor or designee within 24 hours after being made aware of the event, according to the procedures in Section 8.5.3 for SAEs. Investigators are also advised that active TB is considered a reportable disease in most countries. These events are to be considered serious only if they meet the definition of an SAE.

8.6. Pharmacokinetics

8.6.1. Evaluations

Venous blood samples of sufficient volume will be collected for measurement of serum concentrations of guselkumab.

Each serum sample will be divided into 3 aliquots (1 each for PK, anti-guselkumab antibodies to guselkumab, and a back-up). Additional information about the collection, handling, and shipment of biological samples can be found in the Laboratory Manual.

8.6.2. Analytical Procedures

Pharmacokinetics

Serum samples will be analyzed to determine concentrations of guselkumab using a validated, specific, and sensitive immunoassay method by or under the supervision of the sponsor. The sponsor, or its designee, under conditions in which the participants' identities remains blinded, will assay these samples.

8.6.3. Pharmacokinetic Parameters and Evaluations

Parameters

Serum samples will be used to evaluate the PK of guselkumab. Serum collected for PK may additionally be used to evaluate safety or efficacy aspects that address concerns arising during or after the study period. Genetic analyses will not be performed on these serum samples. Participant confidentiality will be maintained.

Pharmacokinetic/Pharmacodynamic Evaluations

The relationship between serum concentrations of guselkumab and efficacy measures or relevant biomarker(s) may be examined where appropriate.

8.7. Genetics and Pharmacogenomics

Participation in pharmacogenomic research is optional. A pharmacogenomic blood sample will be collected only from participants who consent separately to this component of the study to allow for pharmacogenomic research, as necessary (where local regulations permit).

Genetic (DNA) variation may be an important contributory factor to interindividual variability in drug response and associated clinical outcomes. Genetic factors may also serve as markers for disease susceptibility and prognosis and may identify population subgroups that respond differently to an intervention.

Whole blood samples of approximately 6 mL will be collected for genetic analyses as specified in the SoA (Section 1.3).

8.8. Biomarkers

Biomarker assessments will be made to examine the biologic response to treatment and to identify biomarkers that are relevant to guselkumab treatment and/or Crohn's disease. Assessments (detailed below) will include the evaluation of relevant biomarkers in serum, whole blood, and ileocolonic biopsy samples, and ileocolonic video biopsy collected as specified in the SoA (Section 1.3), where local regulations permit. Digital images of biopsy histology slides and endoscopy videos may be used to support exploratory research to develop artificial intelligence algorithms to aide in the evaluation of mucosal improvement in Crohn's disease.

Data collected from these samples will be used for exploratory research that will include the following objectives:

- 1. To understand the molecular effects of guselkumab treatment.
- 2. To understand CD pathogenesis.
- 3. To understand why an individual participant may respond differently to guselkumab.
- 4. To understand the impact of treatment with guselkumab on intestinal inflammation.
- 5. To develop diagnostic tests to identify CD populations, and IBD patients in general, that may be responsive or nonresponsive to treatment with guselkumab.

Stopping Analysis

Biomarker analyses are dependent upon the availability of appropriate biomarker assays and clinical response rates. Biomarker analysis may be deferred or not performed, if during or at the end of the study, it becomes clear that the analysis will not have sufficient scientific value for biomarker evaluation, or if there are not enough samples or responders to allow for adequate biomarker evaluation. In the event the study is terminated early or shows poor clinical efficacy, completion of biomarker assessments is based on justification and intended utility of the data.

8.8.1. Whole-Blood-based Biomarkers

Whole blood samples will be collected from all participants to assess the effect of study intervention on RNA expression profiles where local regulations permit. Whole blood analyses may also examine RNA expression associated with the pathogenesis of CD. Transcriptome studies may be conducted using RNA sequencing, and/or alternative equivalent technologies, which facilitates the simultaneous measurement of the relative abundances of thousands of RNA species resulting in a transcriptome profile for each blood sample. This will enable the evaluation of

changes in transcriptome profiles that may correlate with biologic response relating to CD or the action of guselkumab.

8.8.2. Mucosal Biopsy (Histology, RNA, and Single Cell Isolation)

Mucosal biopsy samples will be collected from all participants during ileocolonoscopy at the times specified in the SoA for histologic assessment, RNA expression analysis, and single cell isolation.

Total RNA will be isolated and used for differential gene expression analyses to identify mRNA or microRNA expression patterns that are relevant to guselkumab treatment and/or CD, and to evaluate markers that can predict therapeutic response. The biopsy samples collected will also be used for the histologic and immunohistochemical assessment of disease and healing. Protein and gene expression will be measured at higher resolution in various immune cell populations isolated from these biopsy samples.

8.8.3. Serum-based Biomarkers

Blood samples for serum-based biomarker analyses will be collected from all participants where local regulations permit. Assays to be performed may include proteins associated with proinflammatory and anti-inflammatory effects, the recruitment and proliferation of cells associated with inflammation and repair, and markers associated with tissue injury or repair. These analyses will include but will not be limited to IL-17A and IL-22.

8.9. Immunogenicity Assessments

Antibodies to guselkumab will be evaluated in serum samples collected from all participants according to the SoA. Additionally, serum samples should also be collected at the final visit from participants who discontinued study intervention or were withdrawn from the study. These samples will be tested by the sponsor or sponsor's designee.

Serum samples will be screened for antibodies binding to guselkumab and the titer of confirmed positive samples will be reported. Other analyses may be performed to verify the stability of antibodies to guselkumab and/or further characterize the immunogenicity of guselkumab.

Samples collected for immunogenicity analyses may additionally be used to evaluate safety or efficacy aspects that address concerns arising during or after the study period. Genetic analyses will not be performed on these serum samples. Participant confidentiality will be maintained.

Analytical Procedures

The detection and characterization of antibodies to guselkumab will be performed using a validated assay method by or under the supervision of the sponsor. Samples may be stored up to 15 years (or according to local regulations) following the last participant's last visit for the study at a facility selected by the sponsor to enable further analysis of immune responses to guselkumab.

9. STATISTICAL CONSIDERATIONS

Statistical analysis will be done by the sponsor or under the authority of the sponsor. A general description of the statistical methods to be used to analyze the efficacy and safety data is outlined below. Specific details will be provided in the Statistical Analysis Plan (SAP).

9.1. Statistical Hypotheses

The primary hypothesis is that guselkumab is superior to placebo in preventing endoscopic recurrence prior to or at Week 48.

9.2. Sample Size Determination

A sample size of 370 participants (185 participants assigned to guselkumab and 185 assigned to placebo) will allow to have at least 90% power to detect 20% differences between guselkumab (30%) and placebo (50%) for endoscopic recurrence rate (primary endpoint) prior to or at Week 48, assuming a 2-sided alpha level of 0.05.

This also will allow at least 90% power to detect 17% differences between guselkumab (37%) and placebo (20%) for clinical remission without disease recurrence at Week 48, assuming a 2-sided alpha level of 0.05. This also will allow 90% power to detect 10% differences between guselkumab (10%) and placebo (20%) for disease recurrence at the main study database lock, all available follow-up of all participants will be used to examine disease recurrence at the time of the database lock.

Endoscopic Recurrence

Assumptions for endoscopic recurrence prior to or at Week 48 were based on previous studies, as described in Table 4.

Table 4:	Endoscopic	Recurrence,	Placebo	Group

Reference	Endoscopic	Sample Size	Placebo rate	Timepoint
	Recurrence definition			
Regueiro 2016	Rutgeerts ≥ i2	150	60%	76 weeks
Yamamoto 2007	Rutgeerts ≥ i2	20	70%	52 weeks
Marteau 2006	Rutgeerts ≥ i2	47	64%	24 weeks
Rutgeerts 2005	Rutgeerts ≥ i2	33	78.8%	52 weeks
Hanauer 2004	Rutgeerts ≥ i2	40	64%	104 weeks
Lochs 2000	Rutgeerts ≥ i2	166	50%	72 weeks
Ewe 1999	Rutgeerts ≥ i2	40	70%	52 weeks
Hellers 1999	Rutgeerts ≥ i2	66	58%	52 weeks

Based on these data above, the endoscopic recurrence rates are assumed to be 50% for placebo and 30% for guselkumab.

To accommodate other potential scenarios, power was calculated based on different assumptions as listed in Table 5.

Table 5: Power to Detect a Treatment Effect Based on Different Scenarios in Endoscopic Recurrence

Event rate at Week 48 for endoscopic recurrence in placebo group	Event rate at Week 48 for endoscopic recurrence in guselkumab group	Difference to be detected	Power
50%	30%	20%	97.7%
50%	25%	25%	99.9%
50%	35%	15%	83.3%
45%	25%	20%	98.3%
40%	20%	20%	98.9%
60%	30%	30%	>99.9%

Clinical Remission without Disease Recurrence

Based on data from PREVENT (20% for placebo, and 36.7 for Infliximab), the rates of clinical remission without disease recurrence are assumed to be 20% for placebo and 37% for guselkumab.

To accommodate other potential scenarios, power was calculated based on different assumptions as listed in Table 6:

Table 6: Power to Detect a Treatment Effect Based on Different Scenarios in Clinical Remission without Disease Recurrence

Event rate at Week 48 for clinical remission without disease recurrence in placebo group	Event rate at Week 48 for clinical remission without disease recurrence in guselkumab group	Difference to be detected	Power
20%	35%	15%	90.0%
20%	36%	16%	93.1%
20%	37%	17%	95.4%

Disease Recurrence

Assumptions for disease recurrence were based on previous studies, as described in Table 7

Table 7:	Disease	Recurrence,	Placebo Group

Reference	Disease Recurrence definition	Sample Size	Placebo rate	Timepoint
Regueiro 2016	CDAI \geq 200 and 70 point increase	150	20%	76 weeks
Ng 2009	Symptoms related to CD associated with endo, lab or radiologic findings	99	28%	52 weeks
Yamamoto 2007	CDAI ≥ 150	20	35%	52 weeks
Rutgeerts 2005	CDAI > 250 or need for rescue medical therapy	40	37.5%	54 weeks
Prantera 2002	CDAI >150, confirmed by endoscopy	22	10.5%	52 weeks
Lochs 2000	CDAI >250 or CDAI > 200 with a 60 point increase	166	31.4%	72 weeks
Hellers 1999	CDAI > 200	66	31%	52 weeks
Ewe 1999	CDAI > 200, rise of 60 points	40	28%	52 weeks
Olaison 1992	CDAI > 150 or HBI ≥4	42	37%	52 weeks

For this endpoint, all follow-up data available at the primary DBL, including beyond one year when available, will be used. Based on this, as well as these data above, the disease recurrence rates are assumed to be 20% for placebo and 10% for guselkumab.

To accommodate other potential scenarios, power was calculated based on different assumptions as listed in Table 8.

Table 8: Power to Detect a Treatment Effect Based on Different Scenarios in Disease Recurrence

Event rate at Week 48 for disease recurrence in placebo group	Event rate at Week 48 for disease recurrence in guselkumab group	Difference to be detected	Power
20%	10%	10%	90.0%
	8%	12%	98.5%
25%	15%	10%	80.9%
	10%	15%	99.7%
30%	15%	15%	98.5%

Accrual time used here is 18 months, total time used here is 30 months. It is expected median follow-up time available at the time of, and thus incorporated in, the main database lock is approximately 18 months. Assuming non-uniform accrual pattern: 25% of participants will be enrolled in the first 6 months, 35% of participants will be enrolled in the next 6 months, and 40% will be enrolled in the last 6 months. Assuming dropout rate is 15% annually. Average duration of follow-up is expected to be approximately 20 months.

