9.4.1. General Considerations

This section is a summary of the planned statistical analyses of the most important endpoints including primary and secondary endpoints. The SAP will include a more technical and detailed description of the statistical analyses described in this section.

Descriptive statistics (eg, mean, median, standard deviation [SD], interquartile [IQ] range, minimum, and maximum) will be used to summarize continuous variables. Counts and percentages will be used to summarize categorical variables. Graphical data displays (eg, line plots) may also be used to summarize data. If significant imbalances were found between treatment groups, additional analyses may be conducted to adjust for the baseline difference. The Kaplan-Meier method will be used to summarize data for time-to-event variables.

The overall Type I error rate will be controlled at the significance level of 0.05 (2-sided). Hierarchical testing will be performed for primary and secondary endpoints, the ordering of which will be described in the SAP.

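### The 90% power for disease recurrence (20% v 10%) is tied to two time points, Week 48 and the main study database lock; it is correct only for Week 48

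*Protocol*

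**What the plan says.** Time to disease recurrence is the second secondary endpoint and step 3 of the testing sequence in SAP 5.4.1.3.

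- **Text of Protocol 9.2.** The trial has "90% power to detect 10% differences between guselkumab (10%) and placebo (20%) for disease recurrence at the main study database lock".
- **Basis for the rates, Protocol 9.2, Disease Recurrence.** "For this endpoint, all follow-up data available at the primary DBL, including beyond one year when available, will be used". The next sentence reads: "Based on this, as well as these data above, the disease recurrence rates are assumed to be 20% for placebo and 10% for guselkumab".
- **Table 8.** The column holding the 20% is headed "Event rate at Week 48 for disease recurrence in placebo group", with a matching Week 48 heading for guselkumab. Its first row gives 90.0% for 20% v 10%.
- **Under Table 8.** "Accrual time used here is 18 months, total time used here is 30 months". Accrual is 25%, 35% and 40% in successive 6-month blocks, dropout is 15% a year, and median follow-up at the lock is about 18 months. Then: "Average duration of follow-up is expected to be approximately 20 months".

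SAP Section 3 repeats the lock wording in its text and the Week 48 headings in its Table 6.

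**The concern.** One stated power is attached to two descriptions of the same pair of rates. The text reads as though 20% and 10% are what will have accumulated by the lock, when participants have been followed for 12 to 30 months. The table says they are what has accumulated by Week 48. Events keep occurring after Week 48, so both descriptions cannot be true of the same hazards, and the event count that drives log-rank power differs between them.

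At stake is whether the third step of the confirmatory sequence has the power claimed for it. Abdominal pain free, time to recurrence of symptoms and steroid-free clinical remission are tested after it, so a weaker step 3 also makes those tests less likely to be reached.

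**Working it through.** **Inputs (Protocol 9.2).** "A sample size of 370 participants (185 participants assigned to guselkumab and 185 assigned to placebo"). Accrual is 25/35/40% over 18 months with the lock at 30 months, so potential follow-up f is 24-30, 18-24 and 12-18 months with weights 0.25, 0.35 and 0.40. Dropout is 15% a year. The disease recurrence sentence gives no alpha, so the rule in Protocol 9.4.1 is used: "The overall Type I error rate will be controlled at the significance level of 0.05 (2-sided"). The test is the log-rank test. Event and dropout times are taken as exponential; this is an assumption of the check.

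**Formulas.** If p is the cumulative rate at T months:

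- event hazard λ = −ln(1 − p)/T; dropout hazard η = −ln(0.85)/12 = 0.01354 per month
- P(event observed by the lock) = λ/(λ + η) × [1 − mean of exp(−(λ + η)f)], the mean taken over the accrual pattern
- D = 185 × (P for placebo + P for guselkumab)
- Schoenfeld power = Φ(√D × |ln HR|/2 − 1.96)
- Freedman power = Φ(√D × (1 − HR)/(1 + HR) − 1.96)

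The hazard ratio is ln(0.9)/ln(0.8) = 0.472 whatever T is, with |ln HR| = 0.750. For 90% power Schoenfeld needs 4 × (1.96 + 1.2816)²/0.750² ≈ 75 events.

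**Reproducing the plan's figure (T = 12 months).** λ = 0.01860 and 0.00878; P = 0.271 and 0.141; events 50.2 + 26.0 = 76.2. Power = Φ(8.73 × 0.375 − 1.96) = Φ(1.315) = 90.6%, against 90.0% printed. A simulated log-rank test gives 89.5%. The five rows of Table 8 come out at 90.6, 98.6, 81.4, 99.7 and 98.5%, against 90.0, 98.5, 80.9, 99.7 and 98.5% printed. With Week 48 taken as 11.04 months, row 1 is 92.4% (Schoenfeld) or 90.0% (Freedman). Table 8 was evidently built on Week 48 or 12-month rates.

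**The same 20% and 10% placed later:**

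| Rates refer to | Events | Schoenfeld | Freedman | Simulation |
|---|---|---|---|---|
| 12 months | 76 | 90.6% | 87.9% | 89.5% |
| 76 weeks (17.5 months) | 55 | 79% | 76% | not run |
| 18 months | 53 | 78.2% | 74.5% | 75.9% |
| 20 months | 48.5 | 74.3% | 70.4% | 71.7% |

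Read as crude proportions with an event by the lock, there are 185 × (0.20 + 0.10) = 55.5 events. Power is then 79.8% (Schoenfeld) or 77.1% (two-proportion test).

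**Other Table 8 rows under a later label (Schoenfeld).** At 18 months the five rows become 78.2, 93.5, 67.2, 97.7 and 93.9%. At 20 months they become 74.3, 91.2, 63.1, 96.5 and 91.8%.

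**How far apart the labels are.** Rates of 20% and 10% at 12 months imply 28.4% and 14.6% at 18 months, and 31.1% and 16.1% at 20 months. Rates of 20% and 10% at 18 months imply 13.8% and 6.8% at 12 months.

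**Follow-up.** Before dropout the mean is 0.25 × 27 + 0.35 × 21 + 0.40 × 15 = 20.1 months, and the median is 19.7. With 15% annual dropout both are about 17.5 months. The printed average of about 20 therefore matches the case without dropout, while the printed median of about 18 is closer to the case with it.

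**The case against.** The strongest reply is that the lock phrase names when the endpoint is analysed, not the horizon of the rates. The objectives in both documents define the endpoint as time to disease recurrence at the main study database lock, and the power sentence goes on to say that all available follow-up will be used then. On that reading the plan assumes Week 48 rates and counts events to the lock, which is what Table 8 computes. This reading is possible and may be what the sponsor meant. It does not account for the later sentences, which rest the assumed rates themselves on follow-up beyond one year.

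A reader might go further in three ways that the documents do not support:

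- **That Table 8 is miscalculated.** It is not; every row reproduces to within about 0.6 points for its own heading.
- **That 20% was taken from the 76-week infliximab trial.** That row is the only 20% in Table 7, but no passage says it is the source. Seven of the nine rows are 52- to 54-week rates, and six of those seven lie between 28% and 37.5%; weighted by sample size the seven average about 30%. A 20% Week 48 placebo rate is below most of that evidence.
- **That the trial is shown to be underpowered for this endpoint.** The 70-80% applies only if the rates are lock rates, and no passage fixes them at 76 weeks, 18 months or 20 months.

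On follow-up, the plan does not say that its 20-month average is net of dropout, and the figure does not enter the power calculation.

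**Conclusion.** The inconsistency holds: the 90% belongs to Week 48 or 12-month rates, while the text of both documents attaches it to the lock. If lock rates are meant, power for 20% v 10% is about 70-80%: 70-79% for rates at 76 weeks to 20 months, and 77-80% as crude proportions by the lock. That rests on 48 to 55 events where about 75 are needed for 90%. Taking the full 30 months as the horizon would give about 54-58%, but typical follow-up is well short of that.

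These figures assume constant hazards, two-sided alpha of 0.05 and the plan's accrual and dropout. Neither they nor the plan's listed power assumptions allow for censoring at cross over for endoscopic recurrence. The primary endpoint's power is unaffected. The SAP Introduction states that the study was discontinued after four participants and keeps the original analyses for reference, so the point concerns the accuracy of the plan.

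**What to change.** State one horizon for 20% and 10% in Protocol 9.2 and SAP Section 3.

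- **If Week 48 is meant:** keep Table 8 and SAP Table 6, and keep the lock as the time of analysis, since that is correct. Write the assumption as *20% v 10% at Week 48, analysed with all follow-up to the main study database lock*. Remove the wording that bases the rates on follow-up beyond one year, and give the reason for choosing 20%.
- **If lock rates are meant:** name the horizon, relabel both tables and restate the power in every row. Row 1 becomes about 70-80%, depending on the horizon.

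As a minor correction in either case, say that the 20-month average follow-up is before dropout (20.1 months), or replace it with about 17.5 months after 15% annual dropout.

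The cost is a text and table edit in two documents, with no change to enrolment. Under the second option the stated power becomes less favourable.

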6.5.1. Open Label / Cross over Treatment

Starting after the Week 8 visit, if disease recurrence is confirmed and the definition as described in Section 9.4.3 is satisfied, participants will cross over to open-label treatment with guselkumab. Similarly, participants who are determined to have endoscopic recurrence by central read on the Week 48 or flare visit ileocolonoscopy will also cross over to open-label treatment; for the optional Week 24 ileocolonoscopy, if the central reader confirms endoscopic recurrence (modified Rutgeerts score of i2a or greater), cross over may be done at the discretion of the principal investigator with the participant's agreement. If a participant does not cross over at Week 24 for endoscopic recurrence but, within the following 16 weeks, develops an increase in CDAI \geq 70 or meets the corticosteroid-related disease recurrence criteria (see Section 9.4.3), then the participant may cross over without the need for a repeat ileocolonoscopy.

As discussed in Section 8, at the cross over visit, participants, regardless of the treatment arm to which they were randomized, will receive guselkumab for 3 doses, followed by maintenance guselkumab This regimen matches the regimen under study in the ongoing Phase 3 study, CRD3004. The induction will be open-label and the participant and investigator will remain blinded to original randomized treatment assignment. Participants will not be allowed to cross over after the Week 128 visit and, while awaiting their confirmatory ileocolonoscopy, regularly scheduled study intervention may be held.

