Endoscopic recurrence defined as a Rutgeerts score ≥ i2 (modified Rutgeerts ≥ i2a) has been adopted as the standard endoscopic outcome in most trials of POCD therapy (D'Haens 2008, Hanauer 2004, Hellers 1999, Reguiero 2016). The International Organization for the Study of Inflammatory Bowel Disease performed a technical review and then a 2-round vote among 14 IBD specialists using the Delphi method, and all agreed on a Rutgeerts' score of i0-i1 as the definition of postoperative endoscopic remission (Vuitton 2016). Additionally, in their recommendations for clinical trial design in POCD, an international panel of IBD experts recommended the modified Rutgeerts score as an appropriate measure of postoperative endoscopic CD activity in regulatory clinical trials (Hanzel 2021). Endoscopic recurrence has also been shown to be a strong predictor of subsequent clinical recurrence. In a meta-analysis of randomized controlled trials, the relative risk for clinical recurrence among patients who experienced endoscopic recurrence was 10.77 (95% CI 4.08-28.40). An accompanying meta-analysis of 11 cohort studies showed an even higher relative risk of 21.33 (95% CI 9.55-47.66). In addition, a single cohort study in the analysis showed a linear relationship between Rutgeerts score and clinical recurrence risk (Ble 2021).

While the study is ongoing, the modified Rutgeerts score as interpreted by the central reader will be used to determine whether endoscopic recurrence has occurred. As discussed in Section 6.5.1, cross over to open-label induction with guselkumab is permissible, at the discretion of the principal investigator, if endoscopic recurrence is confirmed on optional Week 24 ileocolonoscopy, and is mandatory after confirmed endoscopic recurrence on Week 48 ileocolonoscopy or after confirmed disease recurrence. If a participant does not cross over at Week 24 for endoscopic recurrence but within the following 16 weeks develops a CDAI in \geq 70 or meets the corticosteroid-related disease recurrence criteria (see Section 9.4.3), then the participant may cross over without the need for a repeat ileocolonoscopy. Results of the video ileocolonoscopies read by the central reader will also be the basis for the primary and secondary analyses of disease and endoscopic recurrence.

Table 3: Modified Rutgeerts Score

Score	Endoscopic Findings
i0	No lesions
i1	< 5 aphthous lesions

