9.4.3. Secondary Endpoints

The first secondary endpoint is clinical remission without disease recurrence at Week 48. The analyses of this endpoint will be performed after the test of the primary endpoint.

- Clinical remission without disease recurrence is a composite endpoint defined by the following:
 - \circ CDAI < 150 at Week 48 and
 - o No endoscopic recurrence as defined by Rutgeerts score < i2 by Week 48 and
 - o Have not experienced a disease recurrence as defined below

The second secondary endpoint is time to disease recurrence. The analyses of this endpoint will be performed after the test of the primary endpoint and the first secondary endpoint.

- Disease Recurrence is a composite endpoint defined by the following:
 - A ≥ 70-point increase from baseline in CDAI score at beyond 8 weeks after randomization; and a CDAI score of ≥ 200 and evidence of endoscopic recurrence. Endoscopic recurrence is defined as a modified Rutgeerts score of ≥ i2a at the anastomotic site or its equivalent elsewhere in the GI tract, unless a stool test for C. difficile toxin or other enteric pathogen is positive;
 - In event of a positive test for enteric pathogen including C. difficile toxin, the underlying infection should be treated and if ileocolonoscopy has not yet been performed, it should only be done when the infection has resolved, and if disease recurrence threshold is still met
 - OR initiation of a physician-prescribed corticosteroids, or an increase in the dose of steroids already being taken (by greater than 5 mg/day), for over one week for the treatment of CD and evidence of endoscopic recurrence as described above, unless a stool test for C. difficile toxin or other enteric pathogen is positive
 - OR a new draining external fistula
 - OR the reopening and draining of a previously existing external fistula
 - OR developing a new internal fistula
 - OR developing a new perianal abscess

• OR developing a new intra-abdominal abscess more than three months after the date of the index surgery

Participants who have confirmed endoscopic recurrence without disease recurrence at Week 24 or Week 48 and cross over to open-label guselkumab treatment will be censored at cross over for the time to disease recurrence endpoint.

Estimands and Estimators

Estimand of Clinical Remission without Disease Recurrence at Week 48

Treatment:

Experimental: Guselkumab at Week 0 and then thereafter through the end of the total study period.

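### The 90.0% power stated for time to disease recurrence leaves out the plan's own Week 48 crossover censoring; with it, power is about 83–87% (12-month rates) or 86–89% (48-week rates)

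*Protocol*

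**What the plan says.** **The power claim.** Protocol Section 9.2 and SAP Section 3 state 90% power for disease recurrence at 20% (placebo) versus 10% (guselkumab), two-sided 0.05, 185 per arm. Table 8 (SAP Table 6) gives 90.0% for that row and four further scenarios. The inputs listed are 18 months of accrual (25%, 35% and 40% in successive six-month blocks), 30 months in total, and this: "Assuming dropout rate is 15% annually. Average duration of follow-up is expected to be approximately 20 months". Follow-up beyond one year is to be used where available.

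**The crossover rule.** Protocol Section 6.5.1 moves people with endoscopic recurrence to the open-label drug: "participants who are determined to have endoscopic recurrence by central read on the Week 48 or flare visit ileocolonoscopy will also cross over". Section 8.1.3 says that crossover "is mandatory after confirmed endoscopic recurrence on Week 48 ileocolonoscopy or after confirmed disease recurrence". Section 9.4.3 states whom the censoring rule covers: "Participants who have confirmed endoscopic recurrence without disease recurrence at Week 24 or Week 48". For that group it provides that those who "cross over to open-label guselkumab treatment will be censored at cross over for the time to disease recurrence endpoint". SAP Section 5.4.1.1 repeats it.

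**The expected size of that group.** Section 9.2 also says that "the endoscopic recurrence rates are assumed to be 50% for placebo and 30% for guselkumab", by Week 48.

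**The time point of the rates.** The Section 9.2 text gives 20% and 10% "for disease recurrence at the main study database lock". The Table 8 column is headed "Event rate at Week 48 for disease recurrence in placebo group".

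**What counts as an event.** Protocol Section 9.4.3 and SAP Section 5.4.1.2.2 count intercurrent events (ICEs) 1–3 as events for this endpoint. Neither document says whether 20% and 10% include them.

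**The concern.** Log-rank power depends on the number of events. Table 8 relies on events that accrue up to the main database lock, well past Week 48 for early enrolees. The plan removes from risk at Week 48 a large group that it expects to exist, and removes more of it from placebo, where most events would occur. If the table ignores this, the expected event count and the power are too high.

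The endpoint is third of six in the fixed testing sequence (SAP Section 5.4.1.3). If it misses, abdominal pain free, time to recurrence of symptoms and steroid-free remission cannot be claimed.

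**Working it through.** **Inputs from the documents.** 185 per arm; two-sided 0.05; accrual 25/35/40% over 18 months; 30 months total; 15% annual dropout; rates as in Table 8; endoscopic recurrence 50%/30%; endoscopy at Weeks 48–51 (months 11.0–11.7).

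**Formulas.** Event hazard λ = −ln(1−p)/T, with T = 12 months or 48 weeks (11.04 months). Dropout hazard μ = −ln(0.85)/12 = 0.0135 per month. For a participant with administrative follow-up F, the chance of an observed event is λ/(λ+μ) × (1 − exp(−(λ+μ)F)), averaged over the accrual pattern. Power by Schoenfeld is Φ(√(D/4) × |ln HR| − 1.96), where D is total events and HR = ln(1−p₁)/ln(1−p₀).

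**Step 1: reproduce Table 8, first row, without crossover.** HR = ln 0.9/ln 0.8 = 0.472, so |ln HR| = 0.750. With 12-month rates, D = 50.2 + 26.0 = 76.2, and √(76.2/4) × 0.750 − 1.96 = 1.31, giving 90.6%. All five rows agree with the stated values within 0.6 points (table below). With 48-week rates the first row has 81.8 events and 92.4%, a worse match.

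**Step 2: add the Week 48 censoring.** For a share c of those still at risk, F becomes min(F, endoscopy month). Two readings of c:
- *Net share*: disease recurrences are counted inside the 50%/30%. First row: (50−20)/(100−20) = 37.5% placebo and (30−10)/(100−10) = 22.2% guselkumab. Other rows use their own rates.
- *Full share*: 50%/30% of those still at risk.

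First row, 12-month rates:
- net share: 67.1–67.9 events, 86.7–87.1%
- full share: 64.1–65.1 events, 85.2–85.7%

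First row, 48-week rates:
- net share: 72.2–73.0 events, 89.0–89.4%
- full share: 68.9–70.1 events, 87.6–88.1%

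Events needed for 90%: 4 × (1.960 + 1.282)²/0.750² ≈ 75.

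| Scenario | Stated | No crossover, 12-month | With censoring, 12-month | With censoring, 48-week |
|---|---|---|---|---|
| 20% v 10% | 90.0% | 90.6% | 85.2–87.1% | 87.6–89.4% |
| 20% v 8% | 98.5% | 98.6% | 96.7–97.4% | 97.6–98.2% |
| 25% v 15% | 80.9% | 81.4% | 74.9–77.8% | 77.8–80.5% |
| 25% v 10% | 99.7% | 99.7% | 99.1–99.4% | 99.4–99.6% |
| 30% v 15% | 98.5% | 98.5% | 96.8–97.8% | 97.7–98.4% |

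**Step 3: log-rank simulation, first row, two sets of 6,000 trials per case.**
- 12-month rates: 88.8% and 89.6% without crossover; 84.9% and 86.2% (net share), 83.2% and 84.3% (full share) with it.
- 48-week rates: 91.3% and 91.4% without; 88.0% and 88.3% (net), 86.7% and 86.8% (full) with it.

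The Monte Carlo standard error is about √(0.87 × 0.13/6000) = 0.4 points. Taking both methods together gives about 83–87% and about 86–89%. By either method the censoring itself costs about 3 to 6 points.

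**The case against.** **Table 8 is not miscalculated.** A reader might infer that the first row misses 90% on its own listed inputs. It does not: those inputs give 90.6% (12-month) or 92.4% (48-week). The fault is a missing input. This stands.

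**The replacement figures need a model that the plan does not state.** The 50%/30% is recurrence up to Week 48, and the planned primary variable also counts ICEs 1–4, so it is not strictly a Week 48 crossover rate. Non-informative censoring is also doubtful: Section 8.1.3 cites a relative risk of 10.77 for clinical recurrence after endoscopic recurrence. This stands as a caveat. But if those without endoscopic recurrence have a lower later hazard, power falls further (81.5% with that hazard halved, 12-month rates, net share). Optional Week 24 crossovers would also lower it.

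**The shortfall can vanish.** With Table 5's 40%/20% scenario, net share and 48-week rates, there are 75.8 events and power is 90.4%. If 20%/10% exclude ICEs 1–3, about 7–11 extra such events (75−68 to 75−64; 12-month rates, same hazard ratio assumed) restore 90%. That is 2–3% of 370. A placebo 12-month rate of about 22–23%, still halved, also restores it, and seven of the nine placebo rates in Table 7 are 28% or higher. All of this stands, and is why the loss is called modest.

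**A different formula might explain 90.0%.** Freedman's formula with 48-week rates also gives 90.0% for the first row, but it fits the 20% v 8% and 25% v 15% rows less well (about 97.8% and 82.0%). With the censoring it gives 84.5–86.5%. The conclusion does not depend on the formula.

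**Two further stronger readings fail.** A reader might infer from the text that 20%/10% apply at database lock, which would mean much lower power. The table header says Week 48, and the five-row match fits rates at about one year, so this is a wording mismatch. A reader might also take the 20-month average as an error because it ignores crossover. The accrual pattern alone gives 20.1 months, and participants who cross over remain in follow-up, so it correctly describes follow-up available at the lock.

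**Conclusion.** The point holds as an omitted assumption with a modest effect. The five-row match shows that dropout was the only loss modelled, while the design imposes a second one at Week 48. At the plan's base case the first row does not keep its stated 90.0%, and the 25% v 15% row falls from 80.9% to about 75–78% (12-month rates) or 78–80% (48-week rates) by Schoenfeld. The other three rows stay at about 96% or more.

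These figures assume constant hazards, non-informative censoring, an unchanged later hazard in those who stay, and 50%/30% read as a net or a full share. The documents do not settle whether uncounted ICE events would offset the loss.

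Power for the primary and first secondary endpoints and type I error are unaffected. SAP Section 1 reports that the study was discontinued after four participants and that the planned analyses no longer apply, so this corrects the plan of record only.

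**What to change.** In Protocol Section 9.2 (Table 8) and SAP Section 3 (Table 6):

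1. Add to the listed power assumptions that participants with endoscopic but no disease recurrence are censored at the Week 48 crossover, at the planned 50%/30%, assumed non-informative.
2. Recompute all rows on that basis. Restate the first row as about 83–87% if the rates are at 12 months, or about 86–89% if they are at Week 48.
3. Use one time point for 20%/10% in both text and table, and say whether the rates include ICEs 1–3.

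The cost is a slightly less favourable stated power. Sample size, conduct and test do not change.
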